## **Bone Marrow Toxicity**

Patients with inadequate hematologic function will be excluded from this study (see Section 4.1.2). Patients receiving study treatment will be regularly monitored for evidence of marrow toxicity with complete blood counts. Treatment may be delayed for hematologic toxicities as described in Section 5.1.7.3.

Transfusion support for anemia and thrombocytopenia is also permitted at the discretion of the treating physician.

## **Immunogenicity**

As with any recombinant antibody, polatuzumab vedotin may elicit an immune response, and patients may develop antibodies against polatuzumab vedotin. Patients will be closely monitored for any potential immune response to polatuzumab vedotin. Appropriate screening, confirmatory, and characterization assays will be employed to assess ATAs before, during, and after the treatment with polatuzumab vedotin.

## **Reproductive Toxicity**

Adverse effects on human reproduction and fertility are anticipated with the administration of polatuzumab vedotin given the mechanism of action of MMAE. Standard exclusion criteria are used to ensure that patients of childbearing potential (male or female) are using adequate contraceptive methods.

## **Specific Gastrointestinal Toxicity**

Diarrhea, constipation, anorexia, nausea, and vomiting have been reported frequently as treatment-emergent adverse events in Studies DCS4968g and GO27834 with polatuzumab vedotin. Diarrhea has been responsible for study drug modification and discontinuations.

## **Hyperglycemia**

Hyperglycemia has been observed in patients treated with polatuzumab vedotin as well as with other ADCs that use the same vc-MMAE platform. Hyperglycemia has been reversible upon holding or discontinuing treatment of the ADCs and/or initiation or adjustment of anti-hyperglycemic medications.

## **Hepatotoxicity**

Hepatotoxicity has been observed in patients treated with polatuzumab vedotin in both the Phase I and II trials. Although the relationship between hepatotoxicity and polatuzumab vedotin has not been definitively determined, transient, dose-related increases in hepatic enzymes were noted in nonclinical rat studies. No hepatotoxicity was noted following administration of the surrogate ADC in cynomolgus monkeys.

Elevations of transaminases have been reported in patients receiving polatuzumab vedotin and have ranged in intensity from Grades 1-3. These have been reversible with and without dose modification.

## **5.1.4 Risks Associated with Lenalidomide**

### **5.1.4.1 Embryo-Fetal Toxicity**

Lenalidomide, a thalidomide analogue, is structurally related to thalidomide, a known human teratogenic active substance that causes severe life-threatening birth defects. In a developmental study in monkeys, lenalidomide caused limb abnormalities similar to birth defects caused by thalidomide in humans. If taken during pregnancy, lenalidomide is expected to have a teratogenic effect in humans.

Lenalidomide must not be taken by patients who are pregnant. In every country where lenalidomide has been approved, a risk minimization plan, which includes a pregnancy prevention program, is in place. Investigators must ensure that all specific local requirements that are applicable to the safe and effective use of lenalidomide are fulfilled prior to administration to patients. The risk minimization plan should be followed by prescribers and by patients using lenalidomide, with one exception: Because lenalidomide will be administered in combination with polatuzumab vedotin and obinutuzumab *or rituximab*, patients must comply with contraceptive measures designed to ensure safe administration of all *four* study treatments, as outlined in Section 4.1.1. Pregnancy testing and counseling should be performed if a patient misses her period or has unusual/*irregular* menstrual bleeding. Treatment with lenalidomide must be discontinued until it is confirmed that the patient is not pregnant.

### **5.1.4.2 Hematologic Toxicity**

Lenalidomide can cause significant neutropenia and thrombocytopenia. Patients should have their complete blood counts monitored weekly for the first 8 weeks and at least monthly thereafter.

### **5.1.4.3 Venous and Arterial Thromboembolism**

Venous thromboembolic events (predominantly deep venous thrombosis and pulmonary embolism) have occurred in patients treated with lenalidomide. Prophylactic anti-thrombotic medicines are recommended, especially in patients with additional thrombotic risk factors. The decision to take prophylactic measures should be made after a careful assessment of a patient's underlying risk factors. Thromboprophylaxis is presented in Section 4.3.2.5.

Patients with known risk factors for thromboembolism, including prior thrombosis, should be closely monitored. Action should be taken to try to minimize all modifiable risk factors (e.g., smoking, hypertension, and hyperlipidemia). Concomitant administration of erythropoietic agents or previous history of thromboembolic events may also increase thrombotic risk in these patients. Therefore, erythropoietic agents, or other agents that may increase the risk of thrombosis (such as hormone replacement therapy), should be used with caution. A hemoglobin concentration of > 12 g/dL should lead to discontinuation of erythropoietic agents.

Patients and physicians are advised to be observant for the signs and symptoms of thromboembolism. Patients should be instructed to seek medical care if they develop symptoms such as shortness of breath, chest pain, or arm or leg swelling.

#### **5.1.4.4 Tumor Flare Reaction**

Tumor flare reaction (TFR) has occurred during investigational use of lenalidomide for treatment of CLL and lymphoma, and is characterized by tender lymph node swelling, low grade fever, pain, and rash. Monitoring and evaluation for TFR are recommended in patients taking lenalidomide. TFR may mimic disease progression. Guidelines for the management of TFR are presented in [Table 19](#).

#### **5.1.4.5 Severe Skin Reactions**

Angioedema and serious dermatologic reactions including SJS and TEN have been reported during treatment with lenalidomide. These events can be fatal. Guidelines for the management of severe skin reactions are presented in [Table 19](#). Patients with a history of erythema multiforme, Grade  $\geq 3$  rash, or blistering following prior treatment with immunomodulatory derivatives (such as thalidomide and lenalidomide) will not be enrolled in the study.

#### **5.1.4.6 Tumor Lysis Syndrome**

Fatal instances of TLS have been reported during treatment with lenalidomide. Patients at risk for TLS are those with high tumor burden prior to treatment. These patients should be monitored closely, and appropriate precautions should be taken.

#### **5.1.4.7 Hepatotoxicity**

Hepatic failure, including fatal cases, has occurred in patients treated with lenalidomide in combination with dexamethasone. The mechanism of drug-induced hepatotoxicity is unknown. Preexisting viral liver disease, elevated baseline liver enzymes, and concomitant medications may be risk factors. Liver enzymes are to be monitored periodically. Guidelines for the management of hepatotoxicity are presented in [Table 19](#).

#### **5.1.4.8 Renal Impairment**

Lenalidomide is substantially excreted by the kidney. Patients with renal impairment (i.e., calculated creatinine clearance  $< 50$  mL/min) will not be enrolled in this study. Renal function will be monitored during the study, and the lenalidomide dose may be adjusted as outlined in Section [5.1.7.2](#) (see [Table 19](#)).

#### **5.1.4.9 Thyroid Disorders**

Cases of hypothyroidism and cases of hyperthyroidism have been reported during treatment with lenalidomide. Optimal control of co-morbid conditions influencing thyroid function is recommended before initiating lenalidomide treatment.

#### **5.1.4.10 Peripheral Neuropathy**

Lenalidomide is structurally related to thalidomide, which is known to induce severe peripheral neuropathy. There was no increase in peripheral neuropathy observed with

the long-term use of lenalidomide for the treatment of newly diagnosed multiple myeloma.

#### **5.1.4.11 Second Primary Malignancies**

Patients with multiple myeloma treated with lenalidomide in studies that included melphalan and SCT had a higher incidence of second primary malignancies, particularly acute myelogenous leukemia and Hodgkin's lymphoma. Patients are to be monitored for the development of second malignancies.

#### **5.1.4.12 Cardiovascular Reactions**

*Cases of serious adverse cardiovascular events, including atrial fibrillation, myocardial infarction, and cardiac failure occurred more frequently in patients with CLL treated with lenalidomide compared to single agent chlorambucil. Patients will be monitored for the development of cardiac toxicities.*

#### **5.1.4.13 Impaired Stem Cell Mobilization**

*Patients have been reported to show a decrease in the number of CD34+ cells collected after treatment with lenalidomide. Early referral to a transplant center is recommended in patients who are autologous SCT candidates.*

### **5.1.5 Risk of Overlapping Toxicities**

The anticipated toxicities from the combined administration of obinutuzumab *or* rituximab with polatuzumab vedotin and lenalidomide are expected to be manageable in the clinical setting and will be closely monitored throughout the study.

Rituximab was safely combined with polatuzumab vedotin in patients with R/R FL or DLBCL. Grade 3 or 4 neutropenia (21%) appeared to be the most important hematologic adverse event associated with this combination. When given as monotherapy for the treatment of patients with R/R B-cell lymphoma, obinutuzumab was associated with 5% Grade 3 or 4 neutropenia. Because obinutuzumab is expected to have an incidence of neutropenia that is higher than that with rituximab monotherapy, there is a risk of increased incidence of neutropenia. Obinutuzumab and polatuzumab vedotin for the treatment of patients with R/R FL or DLBCL is currently being assessed in Study GO27834. As these new data emerge, they will be assessed and applied to update this study if required.

Lenalidomide has also been associated with hematologic adverse events, including neutropenia. When lenalidomide was combined with obinutuzumab, the incidence of Grade 3 or 4 neutropenia was reported to be 33.3% ([Morschhauser et al. 2014b](#)). Therefore, the combination of G+Pola+Len is anticipated to result in overlapping hematologic toxicity, for which patients will be closely monitored. Guidelines for the management of patients who develop hematologic toxicities are provided in Sections [5.1.7.3](#) and [5.1.7.4](#). In addition to the standard hematologic monitoring, patients enrolled in this study will be closely monitored for evidence of infections.

Because both polatuzumab vedotin and lenalidomide have been associated with a risk of peripheral sensory neuropathy, it is unknown whether this risk may be increased when they are combined. Therefore, peripheral neuropathy will be closely monitored, and guidelines for management for patients who develop neurotoxicity (i.e., peripheral neuropathy, sensory and/or motor) are provided in Sections 5.1.3.1 and 5.1.4.10, and in Table 19.

There is an identified risk of TLS if treated with obinutuzumab, *rituximab*, or lenalidomide and a theoretical risk if treated with polatuzumab vedotin because these agents can result in the rapid destruction of a large number of tumor cells. Therefore, overlapping toxicity in regard to TLS cannot be excluded. Guidelines for management of patients who develop TLS are provided in Table 19.

*Both rituximab and lenalidomide have been associated with dermatologic reactions such as SJS and TEN, and the risk of overlapping toxicities will be monitored. Guidelines for management of patients who develop dermatologic toxicities are provided in Table 19.*

### **5.1.6 Risk of Drug-Drug Interactions**

The risk for clinically relevant PK DDIs between study treatments is low. First, obinutuzumab, *rituximab*, and polatuzumab vedotin are not anticipated to interact directly with CYP isoforms or other drug–metabolizing enzymes or drug transporters. Cytokine modulation may be considered as an indirect mechanism through which a monoclonal antibody could alter CYP expression. However, treatment with obinutuzumab results in only transient increases in cytokine levels after the first infusion, and no increases are observed after subsequent infusions. In vitro (human PBMCs) and in vivo (cynomolgus monkeys) treatment with anti-CD79 antibodies (i.e., the same antigen target as polatuzumab vedotin) showed a low risk for release of systemic pro-inflammatory cytokines. Taken together, these results suggest that both obinutuzumab and polatuzumab vedotin are unlikely to precipitate DDIs via indirect effects on cytokines.

Second, lenalidomide is primarily excreted in the urine. Lenalidomide is not a substrate, inhibitor, or inducer of the CYP group of enzymes (Kumar et al. 2009). In vitro, the MMAE component of polatuzumab vedotin is mainly metabolized by CYP3A4, and it is mainly eliminated by biliary secretion in vivo. Both lenalidomide and MMAE are substrates but not inhibitors of P-gp. Owing to the different elimination pathways for lenalidomide and MMAE, the risk of CYP-mediated and transporter-mediated DDI risk is low when polatuzumab vedotin is combined with lenalidomide.

In addition, simulation results suggest that unconjugated MMAE exposure is likely to be altered by <50% when polatuzumab vedotin is co-administered with strong CYP3A inhibitors or inducers. Therefore, patients who receive concomitant medications that are strong CYP3A or P-gp inhibitors should be closely monitored for adverse reactions.

In summary, clinically relevant PK DDIs are unlikely to occur between lenalidomide, obinutuzumab, *rituximab*, and polatuzumab vedotin.

### 5.1.7 Management of Specific Adverse Events

Study treatment may be delayed for toxicity for a maximum amount of time, as specified in [Table 17](#), [Table 18](#), and [Table 19](#). If study treatment is delayed for longer than the specified maximum amount of time, study treatment will be permanently discontinued. When a treatment cycle is delayed because of toxicity resulting from any component of the regimen, all study treatment should be held and resumed together to remain synchronized. If one drug is discontinued, treatment with the other two drugs may be continued for patients experiencing clinical benefit as determined by the investigator after discussing with the Medical Monitor.

Treatment delays apply to all toxicities described below; dose modifications apply only to toxicities that are considered to be related to lenalidomide or polatuzumab vedotin (only for peripheral neuropathy). There will be no dose reductions of obinutuzumab or *rituximab*. *For patients receiving obinutuzumab, if toxicity occurs before Cycle 1 Day 8 or Cycle 1 Day 15, these doses of obinutuzumab will not be skipped but given after resolution of toxicity.*

#### 5.1.7.1 Polatuzumab Vedotin Dose-Reduction Steps

The dose of polatuzumab vedotin may be reduced *due to neurotoxicity only* according to the following dose reduction steps based on the starting dose (see [Table 15](#) and [Table 19](#)).

**Table 15 Polatuzumab Vedotin Dose-Reduction Steps**

Starting Dose	Dose Reduction	
	Step 1	Step 2
1.8 mg/kg	1.4 mg/kg	none
1.4 mg/kg	none	none

#### 5.1.7.2 Lenalidomide Dose-Reduction Steps

The dose of lenalidomide may be reduced in 5-mg increments one or two times *during induction or post-induction*, depending on the starting dose, as outlined in [Table 16](#). There will be no more than one dose reduction per treatment cycle. *If the lenalidomide dose is reduced to 5 mg during induction, the maintenance or consolidation dose may be escalated to start at 10 mg in post-induction if considered safe per investigator judgment in consultation with the Sponsor. In all other cases, if the lenalidomide dose is reduced, re-escalation is not permitted.*

**Table 16 Lenalidomide Dose-Reduction Steps**

Starting Dose	Dose Reduction	
	Step 1	Step 2
20 mg	15 mg	10 mg
15 mg	10 mg	5 mg
10 mg	5 mg	none

If a lenalidomide-related toxicity occurs during lenalidomide treatment (i.e., before Day 21 of the cycle), lenalidomide must be withheld until criteria for recovery have been met (i.e., improves to Grade  $\leq 2$  or baseline values).

If recovery is observed prior or on Day 15 of the cycle, lenalidomide may be resumed at the same dose for the remainder of the cycle (through Day 21; missed doses will not be made up) at the discretion of the investigator. If the investigator considers that resuming lenalidomide at the same dose within the cycle represents an unacceptable risk for the patient, lenalidomide shall be resumed at reduced dose or withheld for the remainder of the cycle. For subsequent cycles, lenalidomide will be resumed at reduced doses.

If recovery is observed after Day 15 of the cycle, lenalidomide will not be resumed for the current cycle. For subsequent cycles, lenalidomide will be resumed at reduced doses.

Guidelines for management of toxicities occurring during induction and post-induction treatment are provided in Sections 5.1.7.3 and 5.1.7.4, respectively.

Grade 3 or 4 hematologic toxicity a,b	
For patients on a lenalidomide dose <math>\geq 10</math> mg who have had one or no prior lenalidomide dose reductions:
 
 
• Withhold study treatment.a
 
• Administer RBCs or platelets as required.
 
• If patient has not already initiated G-CSF, initiate prophylactic G-CSF for current and subsequent cycles.
 
• For patients who develop platelet count of <math>< 20,000/\mu\text{L}</math> while receiving LMWH, reduce the dose of LMWH. For patients who develop platelet count of <math>< 20,000/\mu\text{L}</math> while receiving platelet inhibitors, consider temporarily withholding platelet inhibitors.
 
• Permanently discontinue study treatment if any of the following events occur: 
 
– Grade 3 or 4 thrombocytopenia that results in significant bleeding per investigator judgment
 
– Recurrent Grade 3 or 4 neutropenia associated with fever <math>> 38^\circ\text{C}</math> lasting <math>> 5</math> days or documented infection despite use of G-CSF and after one lenalidomide dose reduction
 
– Recurrent Grade 4 neutropenia or thrombocytopenia lasting <math>> 7</math> days despite use of G-CSF (for neutropenia) and after one lenalidomide dose reduction
 
 
 
• If improvement to Grade <math>\leq 2</math> or baseline <math>\leq 14</math> days after the scheduled date for the next cycle, resume obinutuzumab or rituximab and polatuzumab vedotin at full dose and resume lenalidomide at current dose.
 
• If improvement to Grade <math>\leq 2</math> or baseline 15–21 days after the scheduled date for the next cycle, resume obinutuzumab or rituximab and polatuzumab vedotin at full dose and resume lenalidomide at a reduced dose per guidelines in Section 5.1.7a,b for current and subsequent cycles.
 
• If study treatment is withheld for <math>> 21</math> days, permanently discontinue study treatment.
 
 
For patients who have had two prior dose reductions:
 
 
• Permanently discontinue study treatment.
 

G=obinutuzumab; G-CSF=granulocyte colony-stimulating factor; LMWH=low-molecular-weight heparin.

a Treatment delays apply to all toxicities; dose modifications apply only to toxicities that are considered to be related to any of the study treatment components. Toxicities that occur during the cycle and subside prior to the next cycle should not trigger the suggested dose modifications.

b If cytopenia is thought to be caused mainly by B-cell lymphoma infiltration of the bone marrow, the investigator may decide not to reduce the lenalidomide dose.

**Table 18 Guidelines for Management of Hematologic Toxicities That Occur on Days 8 and 15 of Cycle 1 for Patients Receiving Obinutuzumab**

Event	Action to Be Taken
Febrile neutropenia or neutropenia with documented infection	
 
• Withhold obinutuzumab and lenalidomide until resolution of fever and infection (as applicable).
 
• If the event is ongoing at Day 1 of Cycle 2, follow instructions in Table 17.
 
 
Note: Obinutuzumab and lenalidomide should not be withheld for asymptomatic neutropenia.

Severe thrombocytopenia a or bleeding	
 
• Withhold obinutuzumab and lenalidomide until platelet count is <math>\geq 50,000/\mu\text{L}</math> and there is resolution of bleeding.
 
• If receiving LMWH, reduce the dose.
 
• If receiving platelet inhibitors, consider temporarily withholding platelet inhibitors.
 
• If the event is ongoing at Day 1 of Cycle 2, follow instructions in Table 17.
 

LMWH=low-molecular-weight heparin.

a Severe thrombocytopenia is defined as a platelet count  $< 10,000/\mu\text{L}$  for patients who are not receiving concomitant anticoagulants or platelet inhibitors and  $< 20,000/\mu\text{L}$  for patients who are receiving concomitant anticoagulants or platelet inhibitors.

### Non-Hematologic Toxicities during Induction Treatment

[Table 19](#) provides guidelines for management of non-hematologic toxicities that occur during induction treatment.

**Table 19 Guidelines for Management of Non-Hematologic Toxicities During Induction**

Event		Action to Be Taken
General guidance for treatment delays and discontinuation		
 
– If study treatment is withheld for >21 days because of a toxicity that is attributable to study treatment, permanently discontinue study treatment.
 
– When a treatment cycle is delayed because of toxicity resulting from any component of the regimen, all study treatment should be held and resumed together to remain synchronized.
 
– If one drug is discontinued, treatment with the other two drugs may be continued for patients experiencing clinical benefit as determined by the investigator after discussion with the Medical Monitor.
 

IRRs and anaphylaxis		
 
– Guidelines for the management of IRRs are provided in Section 4.3.2.1 for obinutuzumab, Section 4.3.2.2 for rituximab, and Section 4.3.2.3 for polatuzumab vedotin.
 
– In case of anaphylaxis, study treatment should be permanently discontinued.
 

Renal toxicity		
 
– Adjust the dose of lenalidomidea as outlined below: 
 
• If creatinine clearance is <math>\geq 30</math> but <math>< 50</math> mL/min, lenalidomide should be given at a dose of 10 mg/day.
 
• If creatinine clearance is <math>< 30</math> mL/min and dialysis is not required, lenalidomide should be given at a dose of 10 mg every other day.
 
• If creatinine clearance is <math>< 30</math> mL/min and dialysis is required, lenalidomide should be given at a dose of 5 mg/day. On dialysis days, the dose should be administered after dialysis.
 
 
 

TLS	Clinical TLS b	
 
– Withhold study treatment.
 
– Correct electrolyte abnormalities, monitor renal function and fluid balance, and administer supportive care, including dialysis as indicated. Rasburicase therapy (if approved by the local health authority) may be administered as needed to reduce hyperuricemia.
 
– If symptoms resolve completely, resume obinutuzumab or rituximab and polatuzumab vedotin at full dose and resume lenalidomide at a reduced dosea per guidelines in Section 5.1.7.2 for current and subsequent cycles.
 
– Perform chemistry panel every other day for the first week after re-initiation of lenalidomide.
 

	Laboratory TLS b	
 
– Withhold study treatment.
 
– Correct electrolyte abnormalities, monitor renal function and fluid balance, and administer supportive care as clinically indicated.
 
– If laboratory abnormalities have resolved completely, resume obinutuzumab or rituximab and polatuzumab vedotin at full dose and resume lenalidomide at a reduced dosea per guidelines in Section 5.1.7.2 for current and subsequent cycles.
 

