**Table 19 Guidelines for Management of Non-Hematologic Toxicities During Induction (cont.)**

Event		Action to Be Taken
Other non-hematologic toxicities (i.e., not described above), excluding alopecia, nausea, and vomiting	Grade 3 or 4	
Grade 4 events
 
 
– Permanently discontinue study treatment.
 
 
Grade 3 events
 
 
– Withhold study treatment.
 
– If improvement to Grade <math>\leq 1</math> or baseline, resume obinutuzumab or rituximab at full dose and, if the event is considered related to lenalidomide, resume lenalidomide accordingly at a reduced dose as per guidelines in Section 5.1.7.2 for current and subsequent cycles.
 
– No more than two dose reductions of lenalidomide are allowed.
 

	Grade 2	
 
– Withhold study treatment.
 
– If improvement to Grade <math>\leq 1</math> or baseline, resume obinutuzumab or rituximab and polatuzumab vedotin at full dose and consider resuming lenalidomide at a reduced dosea per guidelines in Section 5.1.7.2 or continue current dose for current and subsequent cycles.
 

CT=computed tomography; DBLCL=diffuse large B-cell lymphoma; FL=follicular lymphoma; G-CSF=granulocyte colony-stimulating factor; IRR=infusion-related reaction; LMWH=low-molecular-weight heparin; NCI CTCAE=National Cancer Institute Common Terminology Criteria for Adverse Events; NSAID=nonsteroidal anti-inflammatory drug; PML=progressive multifocal leukoencephalopathy; SJS = Stevens-Johnson syndrome; TEN = toxic epidermal necrolysis; TLS=tumor lysis syndrome; ULN=upper limit of normal.

a Dose modifications apply only to events that are considered to be related to lenalidomide.

b According to Cairo-Bishop classification system.

c Graded according to NCI CTCAE, Version 3.0.

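### Read literally, Table 19's clearance-based lenalidomide doses apply only to renal decline judged lenalidomide-related, although the protocol's reason for adjusting is renal excretion

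*Combined protocol and SAP*

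**What the plan says.** Section 5.1.4.8 gives the reason for renal dosing: "Lenalidomide is substantially excreted by the kidney". It then says "Renal function will be monitored during the study, and the lenalidomide dose may be adjusted as outlined in Section" 5.1.7.2, with a cross-reference to Table 19.

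Table 19 (induction, non-hematologic toxicities) has a renal toxicity row that begins "Adjust the dose of lenalidomide", with marker a on the last word. Its three bullets are conditioned only on creatinine clearance and dialysis:

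- 30 to below 50 mL/min: 10 mg/day
- below 30 mL/min without dialysis: 10 mg every other day
- below 30 mL/min with dialysis: 5 mg/day

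Footnote a reads "Dose modifications apply only to events that are considered to be related to lenalidomide". Section 5.1.7, which governs the tables that follow it, says in body text that treatment delays apply to every toxicity, but that "dose modifications apply only to toxicities that are considered to be related to lenalidomide or polatuzumab vedotin (only for peripheral neuropathy"). Section 5.3.4 has causality judged separately for each drug.

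**The concern.** A rule that exists because the kidney clears the drug should be triggered by the clearance. What lowered the clearance makes no difference to how fast lenalidomide leaves the body. As written, the trigger also requires a judgment that lenalidomide caused the decline. For a decline put down to something else, leaving the assigned induction dose unchanged would comply with both footnote a and Section 5.1.7, yet could exceed the dose that Table 19 itself sets for that clearance. Two sites could dose the same clearance differently because they attribute it differently. Lenalidomide can cause significant neutropenia and thrombocytopenia (Section 5.1.4.2), so excess dose matters for safety.

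**Working it through.** The plan states no figure to reproduce. The check is a comparison of texts, followed by simple dose ratios.

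**Step 1: does the relatedness limit reach the renal row?** Yes, by two routes. Marker a on the row's opening leads to footnote a. Section 5.1.7 states the limit independently of any marker; its only other limb is polatuzumab vedotin for peripheral neuropathy.

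**Step 2: is the renal row exempted anywhere?** No exemption was found.

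- Section 5.1.4.8 carries no relatedness condition, but it is permissive (the dose may be adjusted) and refers the reader back to Table 19, where the limit sits.
- Footnote a of Table 17 is wider, covering toxicity related to any study drug, but it belongs to the hematologic table.
- The Table 19 row for other non-hematologic toxicities covers only events not already described, so it does not supply a withholding rule for the renal decline itself.
- The instruction in Section 5.1.7.2 to withhold lenalidomide until recovery is also confined to lenalidomide-related toxicity.

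For an unrelated decline, the text therefore leaves treatment delay under Section 5.1.7 and the permissive sentence in Section 5.1.4.8.

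**Step 3: size, if the assigned induction dose continues.**

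Inputs: assigned doses of 10, 15 or 20 mg/day (Tables 3 and 8) and the tabled doses from the renal row. Below 30 mL/min the tabled average is 10/2 = 5 mg/day without dialysis, and 5 mg/day with it.

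Ratio = assigned daily dose / tabled daily dose.

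| Assigned dose | Cohorts | 30 to <50 mL/min | <30 mL/min |
|---|---|---|---|
| 10 mg | FL 1, 2; DLBCL A | 10/10 = 1.0 | 10/5 = 2 |
| 15 mg | FL 3, 4; DLBCL B | 15/10 = 1.5 | 15/5 = 3 |
| 20 mg | FL 5, 6; DLBCL C | 20/10 = 2.0 | 20/5 = 4 |

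The lower-band figures use the simple average of 5 mg/day. Counted over a full Day 1–21 course, alternate-day dosing from Day 1 gives 11 doses, or 110 mg, and the ratios become 210/110 = 1.9, 315/110 = 2.9 and 420/110 = 3.8. The picture is the same.

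The expansion phase uses the recommended Phase II dose, so whichever row matches that dose applies there too.

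**The case against.** The strongest reply is that the text can be reconciled. The three bullets name only clearance and dialysis, and Section 5.1.4.8 gives excretion as the reason with no causal condition. Marker a is also loosely placed elsewhere in Table 19. It sits on the instruction to withhold treatment in the PML and neurotoxicity rows, where a relatedness limit would contradict the statement in Section 5.1.7 that delays apply to every toxicity. It also sits on the discontinuation of polatuzumab vedotin. A marker that cannot be taken literally there is weak evidence for a literal reading here. Much of this stands: many investigators would probably discount the marker and adjust. It does not remove the conflict, because Section 5.1.7 states the limit without the marker and Section 5.1.4.8 only permits adjustment and points back to Table 19.

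The second reply is that the excess needs a chain of conditions. The patient must have an on-study fall below 50 mL/min (below 30 for the largest ratios), attributed to another cause, with no delay and an investigator who applies the limit. At 10 mg the fall must be below 30 mL/min. Calculated clearance is in the routine chemistry panel, so a decline would be seen. All of this stands, and it limits the weight of the point.

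A reader might also infer that the general reductions in Section 5.1.7.2 ("The dose of lenalidomide may be reduced in 5-mg increments one or two times") are a partial fallback that still leaves a 20-mg patient above the tabled dose. The documents do not support that. A 5-mg step for an unrelated decline is itself a dose modification and falls under the same limit. Either the limit is applied and no step is available, or it is relaxed and the clearance bands are available as well.

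**Conclusion.** The conflict is real and confined to wording. Footnote a and Section 5.1.7, followed as written, switch off the clearance-based doses for a renal decline not attributed to lenalidomide, against the protocol's stated reason for having them. If the assigned induction dose continues, the excess is none, 1.5 or 2.0 times the tabled dose at 30 to below 50 mL/min, and about 2, 3 or 4 times below 30 mL/min. This rests on the literal reading and on dosing continuing. The documents give no frequency for such declines and none is assumed; the combination of conditions suggests they would be few. No endpoint, sample size or analysis is affected. The change should be made because it costs little and improves safety.

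Three stronger readings are tempting and are not supported:

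- **That patients will be overdosed.** Section 5.1.4.8 allows adjustment and Section 5.1.7 allows delay, so the text creates the possibility only.
- **That the renal failure after gastrointestinal hemorrhage in Section 5.3.5.3 shows such a case.** That is an example of how to record events, and a severe hemorrhage would itself bring withholding or discontinuation under Table 19.
- **That patients can enter with low clearance under the lymphoma exception in Section 4.1.2.** Section 5.1.4.8 says that patients below 50 mL/min "will not be enrolled in this study", so this is not a firm example.

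**What to change.** 1. In the Table 19 renal row, remove marker a and state that the doses apply by creatinine clearance regardless of cause, as upper limits, so that a patient already on a lower dose is not raised.
2. In Section 5.1.7, add to the relatedness sentence an exception such as: except lenalidomide dosing by creatinine clearance, which applies regardless of cause.

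Both edits are needed, because Section 5.1.7 would still impose the limit if only the marker were removed.

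Optional and separate: Table 20 carries neither marker a nor clearance bands, so the lack of a clearance-based dose after induction is a different gap. One line making the same doses a ceiling during maintenance and consolidation would close it.

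The cost is a few words in two places, or three with the optional line. No dose value, visit or test changes.
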